## 8.7 Monitoring Period

Continuous monitoring from either Capnostream™ 20p or Nellcor Monitoring Systems will be performed on all patients for a minimum of 24 hours. The monitoring period will last up to patient's full mobilization or up to a maximum of 72 hours, if the patient is still bed-ridden after two days post-surgery.

The monitoring period will start for patients once they arrive on the ward. For patients who are determined to be at high risk due to opioid therapy and not due to other pre-existing factors, monitoring of capnography and pulse oximeter data will start only after opioid therapy has been initiated.

Monitoring may be discontinued if the patient is discharged from the hospital ward.

During Phase I the alarm feature of the monitoring devices will be silenced and the screen information blinded. A regular check during the monitoring period should be completed to ensure the etCO2 filter line and SpO2 sensors are appropriately fitted on the patient.

During Phase II the medical staff will be instructed to respond to alarm feature of the monitoring devices and their screen will be open. A guideline will be created to instruct the nurses in responding to alarms and changes in the monitored parameters. An alarm will be considered a false positive by the observer if the SpO2 sensor or the etCO2 filter line is off the patient or misplaced. Alarms will be considered true positive if the SpO2 sensor and etCO2 filter line placement is correct: observations on patient activity and subsequent interventions will be recorded in the eCRF to identify clinically significant or insignificant alarmed events. As an example, patient activities such as talking, eating or gripping a book with the SpO2 sensor compressed will be marked as true positive with details of the activity recorded to identify the alarmed event as potentially clinically insignificant if no medical intervention was taken. The Monitoring eCRF will be completed to document:

- Care pathway (location/transfer within hospital)
- Alarm threshold applied to the monitor (to be collected during the Monitoring Phase II only for each measured parameter, PR, RR, SpO2 and EtO2).
- Systolic blood pressure and level of consciousness using the AVPU scale to allow the retrospective NEWS analysis
- Monitoring duration
- Vital signs
- Supplemental oxygen use
- Medications
- Product information
- Alarm classification by the study nurses (clinically significant or insignificant)
- Action taken in reaction to device alarm feature
- Adverse Events (as described in Section 10.2)

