## 4. Objectives and Endpoints

### 4.1. Objectives

#### 4.1.1. Primary Objective and Endpoint

The primary objective of this study is to quantify the incidence of RC markers in high risk postsurgical patients, using a system comprised of two continuous monitoring devices, connected to a remote monitoring platform.

The occurrence of at least one of the following RC markers will be considered as primary endpoint for patients monitored by Capnostream 20p during both study Phases:

1. SpO2 ≤ 90% for ≥ 3 minutes.
2. RR ≤ 8 or ≥ 22 bpm for ≥ 3 minutes.
3. etCO2 ≤ 15 or ≥ 60 mmHg for ≥ 3 minutes.
4. Apnea episode lasting > 30 seconds.

The occurrence of at least one of the following RC markers will be considered as primary endpoint for patients monitored by PM1000N-RR during both study Phases:

1. SpO2 ≤ 90% for ≥ 3 minutes.
2. RR ≤ 8 or ≥ 22 bpm for ≥ 3 minutes.

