## 12.3 Analysis of clinical data

Patient demographics and baseline characteristics will be presented using appropriate summary statistics. This includes mean and standard deviation, minimum, maximum and median with the interquartile range [IQR] for continuous variables and counts and percentages for categorical variables. Summary statistics will be reported with maximum 2 decimals, as appropriate. The SAS software (SAS Institute Inc., Cary, NC, USA) will be used to perform statistical analyses. Statistical tests will be based on a two-sided significance level of 0.05. Graphical representations will be used as deemed appropriate. No adjustments for multiple comparisons or multiple look at data will be performed. Outliers and influential observations will be identified via graphical plots and according to study team decision the analysis could be repeated excluding potential outliers. In case of missing data, no imputation method will be implemented for analysis.

The Full Analysis Set (FAS) will be used for primary final analysis. Any patient who does not satisfying the inclusion/exclusion criteria will be eliminate from the FAS population. Details of endpoints analyses and additional analysis will be described in the Statistical Analysis Plan. The analyses of primary objective on the proportion of patient with at least one RC markers will be reported together with their 95% confidence intervals and separately for each arm and phase of the study (see primary endpoint definition). When comparison of clinical primary outcomes is conducted the propensity score methods could be used to control for biases and confounding which may be due to the nature of this study. The

difference between the two groups within phase and between phases within groups will be analyzed by means of unpaired t-test or Mann-Whitney test according to the normal or non-normal distribution. For one secondary outcome the logistic regression model will be used to check potential predictors. Bivariate odds ratios (ORs) and 95% confidence intervals (95% CIs) will be estimated for each predictor. A multivariate logistic regression model will be performed according to univariate model's results. Other secondary outcomes will be performed using sensitivity and specificity analysis.

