## 7.9. Evaluation of Objectives

### 7.9.1. Primary Endpoint

The Primary Endpoint of the Study is to quantify the incidence of RC markers in high risk postsurgical patients, using a system comprised of two continuous monitoring devices, connected to a remote monitoring platform. The proportion and rate of “At least one RC marker” event will be calculated and reported.

The “At least one RC marker” event is defined as the occurrence of at least one of the following RC markers:

1.  $\text{SpO}_2 \leq 90\%$  for  $\geq 3$  minutes (or  $\text{SpO}_2 \leq 90\%$  for  $< 3$  min with an action taken);
2.  $\text{RR} \leq 8$  or  $\geq 22$  bpm for  $\geq 3$  minutes (or  $\text{RR} \leq 8$  or  $\geq 22$  bpm for  $< 3$  min with an action taken);
3.  $\text{EtCO}_2 \leq 15$  or  $\geq 60$  mmHg for  $\geq 3$  minutes (or  $\text{EtCO}_2 \leq 15$  or  $\geq 60$  mmHg for  $< 3$  min with an action taken);
4. Apnea episode lasting  $> 30$  seconds.

For patients monitored by PM1000N, only RC markers #1 and #2 will be considered.

RC determination will be assessed by a physician belonging to the “other” site (cross assessment by the sites). This assessment will be made by the analysis of both device and clinical data for each patient. For each patient all potential RC episodes will be derived using the Detection Tool (see Section 10.1) and will be submitted to the other site’s physician in order to adjudicate the potential RC episodes starting from episodes most likely to be RC. The adjudication will stop at the first RC occurring per patient.

The Events’ rates will be computed as (total number of “At least one RC marker” event)/(total number of time-person in PPS) and will be reported separately for each arm and phase of the study. Events’ rates will be displayed together with their 95% confidence interval (95%CI).

If the number of episode per patient result unbalanced, adjusted rates will be reported using the GEE model, together with their 95% confidence interval (95%CI).

If appropriate, also the events’ rates for each RC marker will be reported separately, for each arm and phase of the study.

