### 7.9.2. Secondary Endpoints

The secondary endpoints are:

1. To compare phases in terms of Primary endpoint incidence;
2. To compare phases in terms of respiratory and SAE incidence, number of ICU transfers and related length of stay, Code blues and RRT responses.
3. To evaluate the rate of clinical early interventions performed by nurse staff to prevent a potential AE, introducing continuous monitoring devices connected to a remote monitoring platform;
4. To evaluate the nurses’ satisfaction related to the monitoring system introducing continuous monitoring devices connected to a remote monitoring platform;
5. To establish the Predictive values of  $\text{EtCO}_2$ , RR,  $\text{SpO}_2$ , plethysmography-derived RR, IPI and EWS in respect to respiratory and other SAE.

In order to evaluate secondary **endpoints #1 and #2**, the incidence of events will be reported together with the comparison between phases, by means of the Chi-square test or Fisher exact test for extreme

proportions, as appropriate. If the monitoring/study exposure results different between phases, also the rates of events will be reported, together with the 95% Poisson Confidence Intervals. The Poisson regression model will be used to calculate the Incidence Rate ratio (IRR), with the d-scale option.

For **endpoint #3**, the rate of clinical early interventions will be calculated as (number of early interventions)/(total time-person in FAS) and it will be reported together with the 95% Poisson Confidence Interval.

Early interventions include, as defined in CRF (Monitoring Period):

1. Stimulated subject to breathe;
2. Repositioned/opened airway;
3. Held or reduced Respiratory Depressive (RD);
4. Added or increased supplemental oxygen;
5. Ventilation support;
6. Other

**Endpoint #4** will be evaluated reporting a summary of the nurses' satisfaction answers.

To identify the predictive values for EtCO2, RR, SpO2, plethysmography-derived RR, IPI and EWS, which can predict respiratory and other SAE, a sensitivity analysis will be performed (**endpoint #5**), and the following parameters will be reported, for each RC marker:

1. **Sensitivity** = 
$$\frac{(\# \text{ of clinical events "Yes" and with RC marker "Yes"})}{(\# \text{ of clinical events "Yes"})} = \frac{TP}{(TP+FN)}$$
2. **PPV** = 
$$\frac{(\# \text{ of clinical events "Yes" and with RC marker "Yes"})}{(\# \text{ of events with RC marker "Yes"})} = \frac{TP}{(TP+FP)}$$

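### Recording lasts from 24 h to mobilisation or 72 h, but the any-RC-marker proportion and its Phase I versus II test have no common window; a first-24 h analysis in the PPS would supply one.

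*Protocol*

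**What the plan says.** - **Recording length.** CIP 8.7 says that continuous monitoring "will be performed on all patients for a minimum of 24 hours" and then: "The monitoring period will last up to patient's full mobilization or up to a maximum of 72 hours". It also provides: "Monitoring may be discontinued if the patient is discharged from the hospital ward", so some records may fall short of 24 h.
- **Endpoint.** CIP 4.1.1: "The occurrence of at least one of the following RC markers will be considered as primary endpoint". Neither the CIP nor SAP 4.1 and 7.9.1 gives an assessment window.
- **Primary analysis.** CIP 12.3: "The analyses of primary objective on the proportion of patient with at least one RC markers will be reported together with their 95% confidence intervals", by arm and phase, in the FAS. SAP 7.9.1 reports a proportion and also a rate, whose denominator is total person-time in the PPS.
- **Adjudication.** SAP 7.9.1 sends candidate episodes to the other site's physician "in order to adjudicate the potential RC episodes starting from episodes most likely to be RC", and stops once one RC has been found for the patient.
- **Phase comparison (endpoint #1).** SAP 7.9.2 uses a Chi-square or Fisher test on incidence, then adds: "If the monitoring/study exposure results different between phases, also the rates of events will be reported", with Poisson intervals and an incidence rate ratio (IRR).
- **Analysis sets.** SAP 7.1.3 uses the PPS for the primary endpoint and endpoint #1 and requires at least 24 h of effective time, meaning cumulative time with valid data. SAP 7.12 allows that cut-off to be changed.

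No analysis restricted to a common window is planned.

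**The concern.** Time to full mobilisation is a post-baseline outcome, and it can stretch the observation window threefold. A patient recorded for 72 h has more opportunity to show a marker than one recorded for 24 h, even at the same underlying risk. A proportion over unequal windows therefore mixes respiratory risk with length of recording.

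Two results are exposed. One is the absolute incidence, which the study exists to quantify. The other is the comparison of Phase I with Phase II. The phases are sequential and separated by at least a month of familiarisation, so ward practice, case mix or alarm-driven care could change time to mobilisation. If it changes, the phase proportions move apart without any change in hazard. The optional propensity score addresses baseline confounding and does not equalise a recording length fixed after baseline.

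**Working it through.** **Inputs.** From the documents: window 24 to 72 h (CIP 8.7); planning proportion 10%, precision 5 points, probability 0.80 of reaching it, 182 evaluable (SAP 6). Assumed here: that the 10% applies per 24 h (the plan attaches no time to it), the shape of the hazard, and every mix of recording lengths.

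**1. The plan's own figure.** Take precision as the half-width of an exact (Clopper-Pearson) 95% interval at p = 0.10. The smallest N with probability at least 0.80 of a half-width of 0.05 or less is 179, and at N = 182 the probability is 0.855. Inflation gives 182 × 1.10 × 1.05 = 210.2. The SAP's 182 and approximately 210 are thus reproduced, and 5 points is the plan's own yardstick for the pooled proportion.

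**2. Proportion against recording length.** With 24 h risk p and constant hazard, P(T) = 1 − (1 − p)^(T/24). If the hazard halves each day, the exponent is 1, 1.25, 1.5 and 1.75 at 24, 36, 48 and 72 h.

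| p = 10% | 24 h | 36 h | 48 h | 72 h |
|---|---|---|---|---|
| Constant hazard | 10.0% | 14.6% | 19.0% | 27.1% |
| Hazard halves daily | 10.0% | 12.3% | 14.6% | 16.8% |

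From 24 to 72 h the shift is 17.1 or 6.8 points; both exceed 5.

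**3. Phase contrast with no true effect.** For common windows of 48 h and 36 h:
- constant hazard: 19.0 − 14.6 = 4.4 points;
- halving hazard: 14.6 − 12.3 = 2.3 points;
- 10% taken as the 48 h risk, constant hazard: 10.0 − (1 − 0.9^0.75 = 7.6) = 2.4 points.

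A mixed example: 60% of Phase I and 30% of Phase II patients are recorded to 72 h, the rest for 24 h, at the same constant hazard.
- Phase I: 0.6 × 27.1 + 0.4 × 10.0 = 20.3%.
- Phase II: 0.3 × 27.1 + 0.7 × 10.0 = 15.1%.

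With an assumed 60 and 120 evaluable patients, a two-sided 0.05 test would reject in about 15% of trials.

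**4. Does the SAP rate remove this?** With at most one event per patient over all recorded days, the expected rate is P(T)/(T/24) per patient-day.

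| 24 h risk | True hazard per day, −ln(1 − p) | 24 h | 48 h | 72 h |
|---|---|---|---|---|
| 10% | 0.105 | 0.100 | 0.095 | 0.090 |
| 30% | 0.357 | 0.300 | 0.255 | 0.219 |

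The rate falls as recording lengthens: little at 10%, markedly at 30%. It moves opposite to the proportion. In the mixed example at a 24 h risk of 30%, the proportions are 51.4% and 40.7%. The rates are 0.514/2.2 = 0.234 in Phase I and 0.407/1.6 = 0.254 in Phase II, where 2.2 and 1.6 are mean recorded days. Phase II looks better on one measure and worse on the other, at identical hazard.

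**5. Person-time ended at the first RC.** Expected person-days are P(T)/hazard, so the rate is P(T) ÷ [P(T)/hazard] = hazard at every T under a constant hazard. The dependence on duration disappears in that case.

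**The case against.** The strongest reply is that the SAP already deals with exposure. The rate in SAP 7.9.1 is unconditional and part of the primary analysis; SAP 7.9.2 adds rates and an IRR when exposure differs; SAP 7.7 tabulates monitoring duration. A reader might infer that the incidence has no time base at all, and the documents do not support that. What stands against the reply is step 4: the one-event numerator over untruncated person-time makes the rate depend on duration as well. The SAP's provision for GEE-adjusted rates suggests that several episodes per patient were contemplated, but adjudication that stops at one RC does not yield them. In addition, slower-recovering patients supply the later hours, so even a well-formed rate may be affected by informative duration.

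Three other strong readings should be set aside.
- **That a 24 h result could never be recovered.** Device memory is retained and the Detection Tool derives all candidate episodes. A patient whose accepted episode falls within 24 h is already classified; the others would need re-adjudication. That is extra work, not lost data.
- **That the device comparison is compromised.** Allocation is randomised within centre in both phases (CIP 8.6), so durations should be similar unless the device itself alters mobilisation. SAP 7.1.1 also says that arms will not be compared.
- **That 4.4 points is the expected bias.** It rests on assumed windows and a constant hazard; other reasonable assumptions roughly halve it.

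It is also fair to say that any marker until mobilisation or 72 h is a coherent quantity for a ward stay. That argues for keeping it beside a fixed-window result. It does not make it suitable as the sole basis for the phase test.

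**Conclusion.** The point holds in limited form. The any-marker proportion and its phase test have no common window, so absolute incidence and the Phase I versus II contrast depend partly on recording length, and the planned rate mitigates this only partly. If 10% is the 24 h risk, a full shift from 24 to 72 h takes the proportion to between 16.8% and 27.1%; a 48 h versus 36 h difference gives about 2.3 to 4.4 points with no true effect. These sizes rest on the assumed 24 h basis of the 10%, the assumed hazard shapes and the assumed durations. The actual effect could be negligible if durations turn out alike in the two phases, although the absolute incidence would still lack a stated window.

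The common 24 h window is available in the PPS only. The FAS, which CIP 12.3 names for the primary analysis, has no such minimum, and SAP 7.12 leaves the cut-off open. This is a cheap improvement to the analysis plan, not a flaw that invalidates the study.

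**What to change.** Leave the monitoring rule as it is.

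1. In SAP 7.9.1 and 7.9.2, add the proportion of PPS patients with at least one RC marker in the first 24 h of effective monitoring, with 95% CI, by arm and phase. Use it for the endpoint #1 phase comparison and show the whole-period proportion beside it.
2. State that this 24 h window stays fixed whatever is done under SAP 7.12, and that it is effective time, not clock time.
3. Reconcile CIP 12.3 (FAS) with SAP 7.1.3 (PPS) for this analysis.
4. Adjudicate candidates in time order. Taking all first-24 h candidates before later ones is enough for the 24 h proportion; full time order is needed to date the first RC.
5. In the rate, end each patient's person-time at the first RC.

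Cost: SAP wording, a different sort order for the adjudication files, and more episodes to adjudicate in some patients. First events after 24 h will appear only in the whole-period result.

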## 8.8 Study Exit

Once the monitoring period has ended the patient will be treated according to the hospital clinical practice. The patient will exit the study upon their discharge from the hospital. Any adverse events (as defined in section 10) observed between the end of the monitoring period and study exit are reportable (as described in section 10.2). The Study Exit eCRF will be used to document that the patient has exited from the study. The reason for study exit will be captured on the Study Exit eCRF. The date of study exit, which should correspond to the date of discharge from the hospital will also be captured here.

If the study exit was for any reason other than normal study completion, refer to section 8.12 of the CIP, for appropriate Study Exit eCRF completion.

## 8.9 Assessment of Safety

Methods and timing for assessing, recording, and analyzing safety parameters, including adverse events are described in the Adverse Event section.

## 8.10 Recording Data

The investigator will clearly mark the clinical records to indicate that the patient is enrolled in this clinical study. The patient's medical records will be used as source documents. Worksheets may serve as source documentation in particular cases if a data field is not in the patient's medical record. Details will be specified in the Monitoring Plan and specific guidance will be provided depending on the site practice.

Capnostream™ 20p or Nellcor Monitoring Systems' device memory data will be the source for the number and duration of RC markers. Device memory data will be exported to a flash memory device for each patient. The memory device will be stored at the investigation site. Device memory data will subsequently be downloaded and transferred to a secure server at Medtronic.

The device data transfer process will be tested and verified during the site initiation process. This will be completed to ensure data quality and identify any process improvements to maximize quality, as needed.

The investigator must ensure accuracy, completeness and timeliness of the data reported in the eCRFs and in all other required reports. Data reported on the eCRFs which are derived from source documents, such as patient medical records, must be consistent with the source documents or the discrepancies need to be justified in a documented rationale, signed and dated by the (principal) investigator, to be filed in the patient file. All baseline and medical history data must be derived from source documents.

Only authorized persons can complete eCRFs. Training will be provided to site personnel on the use of data collection tools. CRFs shall be electronically signed by investigators (physician) or by authorized site staff as specified on the Delegated Tasks List. The final version of eCRFs will be provided to the investigation sites when the investigational site has been declared ready for the study.

It is expected that eCRF will be completed within 15 days from the performed visit or as soon as source documents are available, except for Serious Adverse Events that require immediate reporting (see Table 3) and for Protocol Deviation requiring pre-approval. A delayed completion of the eCRF will not be considered a Protocol Deviation.

Sponsor study personnel will review all collected data and create data queries for missing data that impacts data analysis. Queries will be sent to the investigator or appropriate support staff for resolution.

Data reported on the eCRFs that are derived from source documents must be consistent with the source documents. Where copies of the original source document as well as print outs of original electronic source documents are retained, these shall be signed and dated by a member of the investigational site team with a statement that it is a true reproduction of the original source document.

## 8.11 Deviation Handling

Deviations are instance(s) of failure to follow, intentionally or unintentionally, the requirements of the CIP. Intentional deviations are not permitted, except where necessary to protect the life or physical well-being of a patient in an emergency situation. All deviations must be documented and explained, regardless of the reason for the deviation. Deviations will be documented on the Protocol Deviation eCRF.

If circumstances permit, the principal investigator is required to obtain prior approval from Medtronic before initiating actions that are considered study deviations. Prior approval from EC or competent authority might also be needed if related to safety, well-being or integrity of scientific data. Prior approval is not always realistic in situations where unforeseen circumstances are beyond the investigator's control. However, also in these cases, the event is considered a deviation and shall be reported.

In any emergency situation the investigator shall exercise his/her judgment to safeguard the patient's interest. Such deviations from the CIP do not require the prior approval of Medtronic. The investigator shall report the deviation as soon as possible to Medtronic and the reviewing EC, if applicable. Medtronic will inform the regulatory authorities, if required.

Repetitive or serious investigator compliance issues may result in the need to initiate a corrective action plan, and in some cases freeze enrollment or ultimately terminate the investigator's participation in the clinical study. Examples of serious investigator compliance issues that could determine site disqualification when repeated are:

- Failure to obtain and/or document informed consent;
- Inadequate device accountability;
- Failure to notify sponsor and or EC of reportable unanticipated adverse device effects, adverse events, device deficiencies, and/or adverse drug reactions within required timelines.

Medtronic is responsible for reviewing deviations, assessing their significance, and identifying any additional corrective and/or preventive actions (e.g. amend the CIP, additional training, terminate the study, etc.).

